## 14. POSSIBLE RISKS AND SIDE EFFECTS; SPECIAL MONITORING DURING INVESTIGATIONAL STUDIES

Some patients may expect to have local injection site reactions. Local reactions consist primarily of mild to moderate pain at the injection site, rash, pruritus, induration, tenderness, vesiculation, abscess formation, ulceration or necrosis at the site of injection, and/or regional lymphadenopathy.

Serious systemic reactions to attributed to DCVax-L have not been observed to date. Mild fever or fatigue has been observed in patients injected with DCVax-L. Systemic reactions may include the following symptoms: sneezing, coughing itching, shortness of breath, abdominal cramps, vomiting, diarrhea, tachycardia, hypotension and respiratory failure in severe cases. Systemic allergic reactions including anaphylaxis must be immediately treated with Epinephrine HCL 1:1000.

The risks to newly diagnosed GBM patients as a result of intradermal (i.d.) administration of DCVax-L in the clinical trial may include the following:

- Fatigue, fever, nausea, vomiting, and citrate toxicity secondary to leukapheresis. Leukapheresis. Leukapheresis procedures for blood collection are well established and controlled.
- Fatigue, fever, nausea and vomiting secondary to treatment of the DC with Leukine® or IL-4. After the culture period the DC are washed vigorously to remove residual Leukine® and IL-4, thus minimizing adverse toxicity.

- Administration of DCVax-L may result in local reactions at site of injection resulting in discomfort, bruising, and/or skin ulceration.
- Administration of DC loaded with cell lysate, such as tumor cell lysate, could theoretically cause autoimmunity due to the presence of self-antigens. However, no signs of autoimmunity were observed in the clinical trials with DCVax-L or other related products in altogether more than 1100 patients (see also sections 2.2 and 4).

Furthermore, patients with GBM, irrespective of their immunization status with DCVax-L, are expected to experience symptoms arising from progression of their disease, which may include any or all of the following: headaches, seizures, motor dysfunctions, speech problems, sensory disturbances, altered consciousness, and other sequelae of brain cancer.

#### 15. CRITERIA FOR ENDPOINT EVALUATIONS

Disease progression is assessed by MRI, including T1, T2 and FLAIR sequences. All images are subject to independent central review following a prospectively formulated review charter.

#### 15.1. DISEASE ASSESSMENT PRIOR TO ENROLLMENT

The following criteria are used to determine disease status at the Baseline Visit. If the patient does not demonstrate disease progression based on the criteria below, the patient will be deemed eligible for enrollment in the trial. If disease progression is determined, the patient will not be randomized into the trial.

- In the case of complete resection during primary therapy, there is a new, measurable tumor at the site of the resected tumor (mass greater than 1 cm [10 mm] on MRI).
- In the case of incomplete resection during primary therapy, there is a ≥ 25% increase in the residual tumor and the recurrent portion of the tumor is at least 1 cm in its longest diameter.
- There is appearance of a new lesion/site at least 1 cm in at least 1 dimension or greater, as measured by MRI at a location separate from the original resected tumor.

## 15.2. DEFINITION OF PROGRESSION AFTER ENROLLMENT

Progression, calculated from the nadir tumor burden (i.e. post operative orBaseline), is defined as one of the following:

- In the case of complete resection during primary therapy: a new measurable tumor at
  the site of the resected tumor, defined as a mass with a longest diameter equal to or
  greater than 1 cm in at least one dimension. If progression is not defined by these
  studies, treatment may proceed and determinations made at the next scheduled MRI.
- In the case of incomplete resection during primary therapy: a 25% increase or greater
  in the residual tumor if the recurrent portion of the tumor is at least 1 cm or greater in
  its longest diameter, measured by MRI and confirmed by scans above as attributable
  to tumor growth;
- If resection is indicated for recurrent disease, while radiographic criteria for progression have not been met: surgical resection, subsequently confirmed as

progressive GBM by Pathology at the clinical site and to be confirmed by independent pathology;

- Appearance of any new lesion/site at least 1 cm in at least one dimension or greater measured by MRI and confirmed by scans above;
- Unequivocal progression of non-measurable disease (either non-enhancing disease seen only on T2/FLAIR images or enhancing disease not meeting size criteria for measurability), such that there is confidence that tumor growth has occurred;
- Death: all deaths are counted as events for the primary endpoint.

Radiographic evidence of disease progression will be evaluated and corroborated by independent radiology review to determine disease progression for purpose of this trial. MRIs to assess disease progression are done every 2 months. Unscheduled MRIs or other testing will be recorded in CRFs/eCRFs. If, during unscheduled procedures, there is evidence of disease progression, it must be confirmed through independent review as described above.

#### 15.3. DEFINITION OF CONFIRMED PROGRESSION AFTER ENROLLMENT

For purposes of the new Secondary Endpoint #2, Confirmed Progressive Disease (cPD) will be defined as initial disease progression determined through independent review (a.k.a. unconfirmed PD), AND also either (i) a new lesion or (ii) any one of the following criteria (modified iRANO criteria):

- A further 25% increase or greater in the sum of bi-perpendicular diameters of enhancing tumor, occurring at least 4 weeks after the initial event of PD/PsPD;
- Significant increase in T2/FLAIR non-enhancing lesion attributable to tumor growth;
- Death (all deaths are counted as events).

A secondary analysis will, in addition to the MRI findings, take into account the clinical status of the patient, as follows:

- Non-temporary increase in steroid dose >2 mg/day not associated with the unconfirmed PD event;
- Significant clinical decline not attributable to other causes;

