#### 3.2.5 Ultimately unconfirmed progression

For the cPFS (confirmed PFS) endpoint, events that have been preliminarily identified as disease progression by MRI (uPD events) are classified as cPD events if subsequent scans or medical review demonstrate further progression. The remaining uPD events will be classified as uuPD events, for ultimately unconfirmed disease progression. These uuPD events will by default include events that are not reflective of actual disease progression and will therefore contain a large proportion of the pseudo-progression events, including those induced by DCVax®-L vaccination, that may have occurred in this study.

A KM plot of the percentage of subjects free of uuPD events versus time by treatment arm is intended to aid in the interpretation of the influence of vaccine-induced, pseudo-progression, if any, on the analysis of the primary and secondary endpoints. One example is that an increase incidence in uuPD events over time in the DCVax®-L treatment group relative to the control group could possibly be an indication of the presence of vaccine-induced, pseudo-progression in the analysis of OS, cPFS and PFS.

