#### 8.4.5 Ultimately unconfirmed progression

A KM plot of the percentage of subjects who had a progression event during the trial and who are free of uuPD events (as defined in Section 3.2.5) versus time by treatment arm is intended to aid in the interpretation of influence of vaccine-induced, pseudo-progression, if any, on the analysis of the primary and secondary endpoints. One example is that an increase incidence over time in the intervention group relative to the control group in uuPD could possibly be an indication of the presence of vaccine-induced, pseudo-progression in the analysis of OS, cPFS and PFS.

Overall survival will be compared between patients who had a progression event during the trial and then experience an uuPD and those that experience a cPD, regardless of treatment group.

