## 8.4. CROSSOVER (OPEN LABEL) ARM

Patients enrolled in the study for whom disease progression is established at any point after randomization (as defined in section 15.2 of this protocol, and verified by independent review) will be offered the opportunity to receive DCVax-L and/or any other established treatment of the physician's choice. All procedures below should be followed. Patients who do not participate in the crossover option of the study will return for an EOT visit and continue to be followed for survival.

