## Study Procedures for Crossover (Open Label) Option:

Patients who, wish to continue in the study after confirmation of disease progression, will have the option to receive DCVax-L under the crossover/open label arm of the study (except in rare cases where they were originally randomized to DCVax-L and have exhausted their supply). Patients enrolled into the crossover arm will be required to follow the same study visit schedule as patients enrolled into the treatment arm of the study (Appendix A1). Patients may be treated with any additional established therapies. For these patients, the **Guidelines for Combination Therapy Approaches** described below should be referenced.

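### Pathology-proven recurrence is missing from the cPD criteria, and progressions that cannot be confirmed fall by default into the class read as rich in pseudo-progression

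*Combined protocol and SAP*

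**What the plan says.** **Initial progression.** Protocol 15.2 lists radiographic criteria. It also accepts a re-resection done before those criteria are met, if the tissue is found to be "progressive GBM by Pathology at the clinical site", with independent pathology to follow. SAP 3.1.3 determines initial progression as for PFS and calls it uPD.

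**Confirmation.** Protocol 15.3 and SAP 1.2.3 require a uPD "AND also either (i) a new lesion or (ii) any one of the following criteria (modified iRANO criteria"). The criteria are a further 25% enhancing growth "occurring at least 4 weeks after the initial event of PD/PsPD"; a second imaging criterion, worded "Significant increase in T2/FLAIR non-enhancing lesion attributable to tumor growth"; and death. Steroid increase and clinical decline enter only a secondary analysis. Pathology is not listed.

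**What is left over.** SAP 3.1.3 censors unconfirmed uPD in cPFS. SAP 3.2.5 allows confirmation by later scans or by medical review, and then: "The remaining uPD events will be classified as uuPD events, for ultimately unconfirmed disease progression". It says that this group will hold much of the trial's pseudo-progression.

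**Treatment and imaging after progression.** For crossover patients, Protocol 8.4 says: "Patients may be treated with any additional established therapies". For the others: "Patients who do not participate in the crossover option of the study will return for an EOT visit and continue to be followed for survival". Crossover patients whose drug runs out also move to survival follow-up after an end-of-treatment (EOT) visit.

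**Use of the label.** SAP 8.4.5 plans a survival comparison that ignores arm and sets uuPD patients against cPD patients: "Overall survival will be compared between patients who had a progression event during the trial and then experience an uuPD and those that experience a" (the quote stops just before the second group is named). SAP 8.4.3 censors TTP at a uuPD. Under SAP 8.3.1 and Table 2, cPFS is tested ahead of within-trial PFS and OS.

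**The concern.** cPFS exists to separate real growth from pseudo-progression. Histology of a resected recurrence bears directly on that question, yet the confirming criteria ignore it. A patient whose progression event is proven recurrent GBM still has to show more growth or a new lesion, or die, after the lesion has been taken out.

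Nor does any rule say how to read a scan taken after new therapy or surgery, or what to do when there is no later scan. Both situations end in uuPD.

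Three analyses are exposed. The first is cPFS, which gates two further tests. The second is the uuPD plot, which is meant to show vaccine-induced pseudo-progression. The third is the uuPD-versus-cPD survival comparison: if re-resected and actively treated patients are filed as uuPD, longer survival in that group could be taken as evidence of pseudo-progression when it partly reflects who was selected for further treatment.

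**Working it through.** **1. Pathology.** Two groups need to be kept apart.
- Progression established by pathology alone. 15.2 applies this route only where radiographic criteria were not met, and asks for independent pathology. 15.3 gives that evidence no confirming weight.
- MRI-defined uPD followed by re-resection. 15.2 does not require independent pathology here. Protocol 9.3 plans molecular and immune assays on tissue from later surgeries, not confirmation of progression. Any pathology report is therefore on record only by chance.

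In both groups the 25% criterion refers to enhancing tumour that has been removed, and no new reference scan is defined.

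**2. Missing or late scans.**
- Without crossover: about 10% of 331 = 33 patients, from the share in the SAP executive summary. This includes patients who never progressed, so it is an upper limit on that reading. SAP 1.2.3 words the 90% as patients who have received DCVax-L, which could include initial treatment; the crossover share would then not be given.
- The EOT visit (Protocol 8.5) includes an MRI, timed 7 to 30 days after the last immunization. It is not tied to the uPD date, so it need not fall 4 weeks or more after uPD.
- With crossover: day 0 may come up to 3 months after progression is confirmed, and Appendix A1 shows the first MRI at month 2. In 28-day months the longest gap is 3 × 28 + 2 × 28 = 140 days (20 weeks). With calendar months for the first part it is about 91 + 56 = 147 days (21 weeks).
- SAP Appendix C censors a progression whose preceding MRI was more than 4.5 months earlier: 4.5 × 28 = 126 days, or 137 in calendar months. If Appendix C governs cPFS (SAP 3.1.3 refers to it) and no unscheduled scan came between, a confirmation at that first crossover MRI could be censored.

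**3. Death.** 15.3 counts every death as confirmation. SAP 3.2.5 does not mention death. Appendix C censors deaths more than 4.5 months after the last MRI, apart from deaths within 2 months of randomization. With exponential survival after progression (assumed), the share alive beyond 4.5 months is 2^(−4.5/median):
- median 5.5 months: 57%
- median 8 months: 68%
- median 12.6 months: 78%

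The outer two are the extremes of SAP Table 6. If 10% to 30% of real progressions had no confirming scan (assumed), the share lost as events would be 10–30% if uPD is censored at once, 0% if any later death confirms, and about 7–20% under Appendix C at a median of 8 months (0.68 × 10% to 0.68 × 30%). If death does confirm, uuPD contains only patients not known to have died, and the SAP 8.4.5 survival comparison becomes circular.

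**4. Scale.** The plan gives no sample size for cPFS. The nearest figure is 248 PFS events (SAP 1.3.1). Schoenfeld: (2.326 + 0.994)² / [(1/3)(2/3)(ln 7/11)²] = 11.03 / 0.0454 = 243, within 2% of 248. Power at 248 events is 84.8% against the stated 84%.

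Equal loss in both arms (true HR 7/11, one-sided 2.409%):

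| Share lost | Events | Power |
|---|---|---|
| 0% | 248 | 91.6% |
| 10% | 223 | 88.6% |
| 20% | 198 | 84.7% |
| 30% | 174 | 79.7% |

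Unequal loss with no true effect: apparent HR = share confirmed on DCVax-L / share confirmed on placebo.

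| Confirmed, DCVax-L v placebo | Apparent HR | One-sided false-positive rate |
|---|---|---|
| 90% v 90% | 1.00 | 2.4% |
| 85% v 90% | 0.94 | 5.7% |
| 80% v 90% | 0.89 | 11.9% |
| 70% v 90% | 0.78 | 36.6% |

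Reversing the last row gives 0.90/0.70 = 1.29. Every share is an assumption.

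**The case against.** Much of the other side's case stands.
- Death is itself a cPD criterion, so read literally a uPD patient who later dies is confirmed. However, no section says whether that event is dated at uPD or at death, and Appendix C can censor it.
- SAP 3.2.5 allows medical review. It is not defined, is absent from 15.3 and is not tied to pathology, but it could rescue some cases.
- New-lesion and T2/FLAIR confirmation carry no stated 4-week wait, so some patients can be confirmed before rescue treatment, or after the enhancing tumour is gone.
- The EOT visit includes an MRI, and crossover patients restart MRI every 2 months. Loss of scheduled imaging mainly concerns the roughly 10% who do not cross over and those whose drug runs out.

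A reader might infer that the misclassification favours DCVax-L, because those patients can exhaust their doses and placebo patients cannot. The documents do not support this. Protocol 8.4 calls exhausted supply rare and gives no other arm-specific bar to crossover. Missing scheduled MRI through non-crossover could not by itself produce a 30% loss: 33 of 232 is 14%, and that would need every non-crossover patient to be on DCVax-L and to have progressed. The hazard ratios above only restate the shares put in.

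**Conclusion.** The pathology gap is plain in the text. 15.2 accepts proven recurrent GBM as progression; 15.3 and SAP 1.2.3 do not accept it as confirmation. Such an event can be left unconfirmed, censored in cPFS and counted as uuPD.

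For uPD followed by new therapy or surgery, or without a later scheduled MRI, the default to uuPD is a risk of misclassification, not a certainty. Its size and its direction by arm cannot be computed from the documents. Equal misclassification costs power; only unequal misclassification biases the comparison, and it could go either way.

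It would also go too far to say that the SAP equates uuPD with pseudo-progression. It says that the group will contain a large part of it. The weakness is that events which could not be assessed are placed in the same group as events that were assessed and did not progress.

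**What to change.** 1. In Protocol 15.3 and SAP 1.2.3 and 3.2.5, add progressive GBM confirmed by pathology at re-resection as a confirming criterion. Use the independent pathology collected under 15.2. For patients re-resected after an MRI-defined uPD, use any pathology on record and report how many results are local only. State the event date.
2. Restrict uuPD to uPD events with an evaluable later scan that shows no further growth. Report the rest by arm as not evaluable for confirmation, outside the uuPD plot and the uuPD-versus-cPD survival comparison. Count them as cPFS events at the uPD date in a sensitivity analysis only.
3. Reconcile Protocol 15.3 with SAP 3.1.3, 3.2.5 and Appendix C on whether and when death confirms, what medical review covers, and how scans after new anticancer treatment are handled.

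The cost is definition wording before lock and unblinding, plus a re-derivation from pathology, concomitant-therapy and MRI dates. Independent pathology may not exist for the second group in item 1. The sensitivity analysis in item 2 moves cPFS back towards PFS and will count some unresolved pseudo-progression as events, possibly not equally by arm, which is why it should not replace the main analysis. No treatment or visit changes.

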#### 15.4. DEFINITION OF TUMOR RESPONSE

Resection of GBM typically focuses on removing the enhancing tissue as that is supposed to be the area of active tumor growth. Incomplete resections result in residual enhancing disease post-surgery and most patients also have non-enhancing disease areas surrounding the enhancing lesion. Tumor response will use pre- and post-randomization measurements of enhancing and non-enhancing disease. Modified RANO criteria will be applied allowing for evaluation of non-measurable disease to determine response rates.

<sup>5 Radbruch et al. 2010: Neuro Oncol. 2011 Dec 6.

## 15.5. TIME TO TUMOR PROGRESSION

Time to tumor progression is assessed from nadir tumor burden (post operative or Baseline) to the date of the first observation of objective disease progression measured by MRI and confirmed if necessary by scans as described above in section 14.2.

Patients who have not progressed by the end of the study will continue to be followed for tumor progression or tumor recurrence, for survival (Section 14.5) and for their medical history.

#### 15.6. SAFETY

Toxicity is monitored and graded according to NCI Common Terminology Criteria for Adverse Events (Appendix F). The overall incidence of AE is compared between the treatment cohort and the placebo cohort.

## 15.7. SURVIVAL TIME

Survival calculated from randomization to death, due to any cause.

Patients enrolled in the study will be followed for survival. If a patient has progressed to the primary end point and was living at last follow-up, the site will contact the patient, as scheduled (see below and Appendices A-C) to ascertain survival status.

Patients who are presumed alive, and who have not returned to the study site for a scheduled visit, will be contacted by the study site at the patient's pre-study contact telephone number to ascertain patient status. These contacts will be attempted weekly for 4 weeks. If no information is obtained as to patient status, a certified letter will be sent to the last known patient address. If no response is returned, then secondary or tertiary contact numbers will be utilized. The telephone numbers of patient locaters will be obtained with the patient's permission at the time of enrollment in the study. Patient locators will be identified by the patient as persons who would be aware of change of address, phone number, employment and/or school. The patient locator will be contacted to ascertain the location and/or status of the enrolled patient. In the event that information cannot be obtained from locator contacts, patient status, as alive or dead, will be tracked. The follow-up of subjects for survival and medical history extends until death regardless of the duration of study medication treatment or follow-up for the primary endpoint.

## 15.8. KARNOFSKY PERFORMANCE STATUS

Patients are graded according to KPS. The performance status over time is compared between patients receiving DCVax-L or placebo.

#### 16. STATISTICAL CONSIDERATIONS

The full statistical considerations underlying the endpoints and intended analyses are described in the Statistical Analysis Plan, which is provided as Appendix H to this protocol. A summary overview is provided below.

This statistical analysis plan (SAP) is intended to serve as the roadmap for evaluating data (Trial Data) acquired in the Phase III clinical trial of Northwest Biotherapeutics, Inc. (NWBT) DCVax®-L autologous dendritic cells (DCs) pulsed with tumor lysate antigen, as adjuvant therapy to standard primary treatments in patients with newly diagnosed and recurrent glioblastoma multiforme (GBM), Protocol No. 020221, v7.0 (the Protocol or the Trial).

Page 36 of 55

This SAP has been jointly developed by three independent biomedical/clinical trial statistical experts. The SAP describes our method for analysing the Trial Data and the impact of DCVax®-L on the course of disease as accurately as possible with endpoints as described below, in accordance with scientific developments that have emerged since inception of the trial.

The original Protocol primary endpoint was to compare progression-free survival (PFS) of the trial treatment arm with a placebo cohort. The original Protocol secondary endpoint was to compare overall survival (OS) of the trial treatment arm with the placebo cohort. However, two major real-world developments took place during the course of the Trial:

- Scientific appreciation of the phenomenon of pseudo-progression advanced, highlighting the
  virtual impossibility of distinguishing radiation-induced oedema, and vaccine-induced
  immune-cell infiltration and/or inflammation, from true disease progression. Until a broadly
  accepted definition of this distinction is settled, the subjectivity of its determination suggests
  that the trial data should be studied in reference to a more objectively ascertained Trial
  endpoint than PFS, which is OS (below); and
- Such a large percentage of patients made use of the crossover option in the Protocol that the original control arm became substantially depleted and insufficient for OS analyses within the Trial. When the Trial began in 2007, per the demand of investigators and patients it was necessary to include a crossover option in the Protocol in order to recruit and retain patients. This crossover option allowed patients from both the DCVax®-L arm and the control arm of the Trial to receive DCVax®-L treatment following progression (recurrence), while they and all other parties (including the Sponsor and investigators) remained blinded as to what treatment they received before crossover. Approximately 90% of all patients in the Trial made use of this crossover, resulting in the substantial depletion of the control arm.

These two key developments require corresponding adaptation of the methodology for evaluating the data, specifically:

- (a) designating survival (OS) as the trial's primary endpoint and first secondary endpoint-as survival is the patients' ultimate goal--while also retaining the original progression-free survival (PFS) criteria as an additional secondary endpoint, to the extent PFS may ultimately be ascertained from analysis of the Trial Data; and
- (b) replacement of the Protocol placebo control cohort with a large, closely matched, independently chosen external control group—in each case as described below:
  - Endpoints: The SAP (Section 1.2) adopts the following endpoints as a basis for demonstrating efficacy:
    - Primary Endpoint: OS relative to external controls.
    - First Secondary Endpoint: OS following recurrence, relative to external controls; and
    - Additional Secondary Endpoints: To the extent demonstrably ascertainable from analysis of the Trial Data, confirmed PFS, and original Protocol endpoints PFS and OS.
  - External Controls: Depletion of the Protocol placebo cohort is addressed in this SAP by comparing primary and secondary endpoint results in the Trial treatment arm with external control cohorts, consistent with the FDA's December 2019 Draft Guidance

Protocol: 020221, v7.0 23SEP2020 Page 37 of 55

on Demonstrating Substantial Evidence of Effectiveness for Human Drug and Biological Products.

The identification of appropriate external controls was done through a systematic literature search which has been conducted by the independent expert firm, York Health Economics Consortium, UK. This independent expert analysis was checked and confirmed with a panel of independent neuro-oncology experts who were not involved in the Trial. In addition, the statistical analysis includes methodologies to ensure matching of these identified external controls to the DCVax®-L trial population based on known prognostic factors, applied by independent statisticians.

